3.2.3 Rationale for patient reported outcomes

The assessment of patient-reported outcomes (PROs) in clinical research provides important insight into how therapies impact the daily lives of patients. Patient reports regarding health-related quality of life have proven more comprehensive than provider-collected data in breast cancer patients ([Oberuggenberger et al 2011](#)). Because olaparib is a new drug about which

little is known regarding toxicity and impact on quality of life, we will use questionnaires to assess overall quality of life, treatment satisfaction and tolerability symptoms in each of the two study arms.

3.2.4 Rationale for health economic data

The assessment of health economic resource use data will provide important information for payers and will be used within economic evaluations of olaparib.

3.2.5 Study Population

Approximately 310 metastatic breast cancer patients with *gBRCA1/2* mutations will be randomised into the study.

All patients recruited in the study will be selected based on the following principle:

- Genetic selection: Documented germline mutation in *BRCA1* or *BRCA2* that is predicted to be deleterious or suspected deleterious (known or predicted to be detrimental/lead to loss of function). Patients with *BRCA1* and/or *BRCA2* mutations that are considered to be non-detrimental (eg, “Variants of uncertain clinical significance” or “Variant of unknown significance” or “Variant, favour polymorphism” or “benign polymorphism,” etc) will not be eligible for the study.

In terms of *BRCA* mutation status, the following scenarios are considered:

- Status known: for patients already known to have a germline *BRCA* loss of function mutation (known as deleterious or suspected deleterious) the exact sequence variant must be recorded on the screening CRF and a copy of the genetic diagnosis available at site. These patients may be randomised into the study based on the known status, however, re-confirmation of the loss of function mutation from a blood sample will be undertaken by a central laboratory, Myriad Genetic Labs Inc.
- Status unknown: The germline *BRCA* mutation status must be determined prior to randomisation as a loss of function mutation i.e. a known deleterious or suspected deleterious mutation

4. PATIENT SELECTION CRITERIA

Investigator(s) should keep a record, the patient screening log, of patients who entered pre-study screening.

Patients with unknown *BRCA* mutation status who are being considered for this trial should be identified early so that the appropriate *BRCA* mutation screening procedures can be put in place in a timely manner. These patients must fulfil all of the criteria marked with an asterisk below prior to *BRCA* mutation testing being carried out.

Each patient should meet all of the inclusion criteria and none of the exclusion criteria for this study prior to randomisation. Under no circumstances can there be exceptions to this rule.

4.1 Inclusion criteria

For inclusion in the study patients should fulfil the following criteria:

1. *Provision of informed consent prior to any study specific procedures
2. *Patients must be male or female ≥ 18 years of age
3. *Histologically or cytologically confirmed breast cancer with evidence of metastatic disease
4. Documented mutation in BRCA1 or BRCA2 that is predicted to be deleterious or suspected deleterious (known or predicted to be detrimental/lead to loss of function) (See Section 3.1)
5. *Patients must have received treatment with an anthracycline (e.g. doxorubicin, epirubicin) unless contraindicated and a taxane (e.g. paclitaxel, docetaxel) in either a neo-adjuvant / adjuvant or metastatic setting.
6. *Patients who have received platinum (cisplatin or carboplatin, either as monotherapy or in combination) for advanced breast cancer are eligible to enter the study provided there has been no evidence of disease progression during the platinum chemotherapy
7. Patients who have received prior platinum based chemotherapy are eligible if platinum was given either as potentially curative treatment for a prior non-breast cancer (eg ovarian cancer) with no evidence of disease for ≥ 5 years prior to study entry or as adjuvant/neoadjuvant treatment for breast cancer provided at least 12 months have elapsed between the last dose of platinum-based treatment and randomization
8. Patients with estrogen and/or progesterone receptor-positive disease must have received and progressed on at least one endocrine therapy (adjuvant or metastatic), or have disease that the treating physician believes to be inappropriate for endocrine therapy
9. At least one lesion (measurable and/or non-measurable) that can be accurately assessed at baseline by CT (MRI where CT is contraindicated) and is suitable for repeated assessment as per RECIST 1.1.
10. Patients must have normal organ and bone marrow function measured within 28 days prior to administration of study treatment as defined below:

- Haemoglobin ≥ 10.0 g/dL with no blood transfusions (packed red blood cells and platelet transfusions) in the past 28 days
 - Absolute neutrophil count (ANC) $\geq 1.5 \times 10^9/L$
 - Platelet count $\geq 100 \times 10^9/L$
 - Total bilirubin ≤ 1.5 x institutional upper limit of normal
 - AST (SGOT)/ALT (SGPT) ≤ 2.5 x institutional upper limit of normal unless liver metastases are present in which case they must be ≤ 5 x ULN
 - Serum or plasma creatinine ≤ 1.5 x institutional upper limit of normal (ULN)
11. *ECOG performance status 0-1 within 21 days of randomisation
12. * Postmenopausal or hysterectomized; women of childbearing potential are eligible with a negative urine or serum pregnancy test documenting evidence of non-childbearing status.
- Postmenopausal is defined as any of the following:
- Age ≥ 60 years
 - Age < 60 years and amenorrhic for 1 year or more in the absence of chemotherapy and/or hormonal treatment
 - luteinising hormone (LH), follicle stimulating hormone (FSH) and plasma oestradiol levels in the postmenopausal range for women under 60 years of age
 - radiation-induced oophorectomy with last menses >1 year ago
 - or surgical sterilisation (bilateral oophorectomy)
13. *Patient is willing and able to comply with the protocol for the duration of the study including undergoing treatment and scheduled visits and examinations
14. Formalin fixed, paraffin embedded (FFPE) tumour sample from the primary tumour if available
- For inclusion in
- (a) the optional exploratory genetic research and/or
 - (b) the optional tumour biopsy research,
- patients must fulfil the following criteria:

- Provision of informed consent for genetic research
- Provision of informed consent for tumour biopsy research

If a patient declines to participate in the optional exploratory genetic research or the optional tumour biopsy research, there will be no penalty or loss of benefit to the patient. The patient will not be excluded from other aspects of the study.

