Medical and surgical history ^b		X							
Family history of cancer		X							
Prior cancer therapies		X							
Inclusion/exclusion criteria	X (all * criteria) ^a	X							
ECOG Performance Status		X					X		X
Vital signs		X	X ^d			X (every 12 weeks)	X	X	
Haematology / clinical chemistry		X	X ^e	X	X	X	X	X	
Physical examination ^f		X	X			X	X	X	
Tumour Assessment (RECIST 1.1)		X ^g				X ^g			
ECG ^h		X							

Table 1 Study Schedule – Screening, On Study Treatment, Discontinuation and Follow-up

Visit Number	Screen PART 1 (Pt with UNKNOWN BRCA status only)	Screen PART 2 (ALL patients)	On treatment Cycle 1			On treatment visits every 3 weeks	Study treatment discontinued	30-Day follow-up	Survival follow-up
			1	8	15				
Day		-28 to 0	1	8	15	Cycle X Day 1			Every 8 weeks
Visit Window				±3d	±3d	±3d	±7d	±7d	±7d
Urinalysis ⁱ		X							
Pregnancy test ^j	X	X	X						
Blood samples BRCA status ^k	X		X ^l						
Adverse Events	X ^m	X	X	X	X	X	X	X	
Concomitant medications including blood transfusions		X	X	X	X	X	X	X	
EORTC QLQ-C30		X ⁿ				X ⁿ (every 6 weeks until progression)			
CTSQ-16						X (every 6 weeks until discontinuation of study treatment)	X		
Healthcare Resource Use ^o			X	X	X	X	X	X	
Pharmacogenetic blood sample (optional)			X						
Archival tumour (mandatory if available) ^t		X							

Table 1 Study Schedule – Screening, On Study Treatment, Discontinuation and Follow-up

Visit Number	Screen PART 1 (Pt with UNKNOWN BRCA status only)	Screen PART 2 (ALL patients)	On treatment Cycle 1			On treatment visits every 3 weeks	Study treatment discontinued	30-Day follow-up	Survival follow-up
Day		-28 to 0	1	8	15	Cycle X Day 1			Every 8 weeks
Visit Window				±3d	±3d	±3d	±7d	±7d	±7d
Tumour biopsy (optional) ^p		X				X Only at progression			
Blood sample for PK analysis (Subset of patients) ^u						X			
Blood samples for biomarker analysis (mandatory) ^q			X			X Only at progression			
Olaparib dosing ^u			Continuous twice daily dosing 						
Eribulin dosing ^v			X	X		X			
Vinorelbine dosing ^w			X	X		X			
Capecitabine dosing ^x			Days 1-14 only 			X			
Subsequent cancer therapy ^r								X	X
Second progression assessment									X
Survival ^s									X
Olaparib dispensed/returned			X			X	X		

^a These screening assessments do not need capturing on the eCRF, but they must be recorded in the patient's notes.

- b Include history of blood transfusion within previous 120 days from start of study treatment and the reasons e.g. bleeding or myelosuppression

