- c It is recommended that patients commence study treatment as soon as possible after randomisation, and ideally within 3 days.
- d If vital signs assessed within 7 days before starting study treatment, it does not need to be repeated on Day 1 of study treatment unless investigator believes that it is likely to have changed significantly.
- e Safety blood samples do not need to be repeated on Day 1 of study treatment if they have been assessed within 7 days before starting study treatment and which must have been 3 weeks after last dose of chemotherapy, unless the investigator believes that it is likely to have changed significantly. Coagulation analysis only required at baseline.
- f Physical examination should be performed according to the schedule, after the baseline assessment it is not necessary to record the details on the eCRF, any clinically significant changes not unequivocally related to disease progression, should be reported as adverse events.
- g Baseline RECIST assessments will be performed using CT scans of the chest, abdomen and pelvis (or MRI where CT is contraindicated) and should be performed no more than 28 days before the start of study treatment and as close as possible to the start of study treatment and prior to randomisation. RECIST follow-up assessments will be performed every 6 weeks (± 1 week) for the first 24 weeks, then every 12 weeks (± 1 week) after randomisation until objective disease progression as defined by RECIST 1.1, irrespective of treatment decisions. Follow-up assessment will include CT assessments of chest, abdomen and pelvis (or MRI where CT is contraindicated) for all patients. Any other sites at which new disease is suspected should also be appropriately imaged. If an unscheduled assessment was performed and the patient has not progressed, every attempt should be made to perform the subsequent assessments at their scheduled visits. Prior to primary analysis for PFS, all scans will be submitted for independent review. If progression is not confirmed at central review an additional RECIST assessment will be requested at the next scheduled visit. Following disease progression further RECIST assessments will not be performed and assessment of disease will be as per local clinical practice.
- h ECG assessments to be completed within 7 days before starting treatment. After screening, ECGs will only be required if clinically indicated.

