4.2 Exclusion criteria

Patients should not enter the study if any of the following exclusion criteria are fulfilled:

1. *Involvement in the planning and/or conduct of the study (applies to AstraZeneca staff/BCA staff and/or staff at the study site).
2. *BRCAl* and/or *BRCAl2* mutations that are considered to be non detrimental (e.g., “Variants of uncertain clinical significance” or “Variant of unknown significance” or “Variant, favour polymorphism” or “benign polymorphism” etc.).
3. Cytotoxic chemotherapy or non-hormonal targeted therapy within 21 days of Cycle 1 Day 1 is not permitted. Endocrine therapy must have been discontinued 7 or more days before Cycle 1 Day 1. Palliative radiotherapy must have been completed 14 or more days before Cycle 1 Day 1. The patient can receive a stable dose of bisphosphonates or denosumab for bone metastases, before and during the study as long as these were started at least 5 days prior to study treatment.
4. *Patients with HER2-positive disease (3+ by IHC or ISH amplified ≥ 2.0).
5. *Previous randomisation in the present study.
6. Exposure to an investigational product within 30 days or 5 half lives (whichever is longer) prior to randomisation
7. *Any previous treatment with a PARP inhibitor, including olaparib.
8. *Patients with second primary cancer, EXCEPTIONS: adequately treated non-melanoma skin cancer, curatively treated in-situ cancer of the cervix, Ductal Carcinoma in Situ (DCIS), stage 1 grade 1 endometrial carcinoma, or other solid tumours including lymphomas (without bone marrow involvement) curatively treated with no evidence of disease for ≥ 5 years prior to study entry.
9. Resting ECG with QTc > 470 msec detected on 2 or more time points within a 24 hour period or family history of long QT syndrome. If ECG demonstrates QTc >470 msec, patient will be eligible only if repeat ECG demonstrates QTc ≤ 470 msec.

10. *Patients cannot have received more than 2 prior lines of cytotoxic chemotherapy for metastatic disease. Prior treatments with hormonal therapy and non-hormonal targeted therapy are allowed and not counted as a prior line of cytotoxic chemotherapy. For the purposes of this protocol, the combination of an aromatase inhibitor and everolimus is not considered cytotoxic chemotherapy.
11. *Concomitant use of known potent CYP3A inhibitors such as ketoconazole, itraconazole, ritonavir, indinavir, saquinavir, telithromycin, clarithromycin and nelfinavir. For further detail refer to Appendix I.

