12. Persistent toxicities (\geq CTCAE grade 2) caused by previous cancer therapy, excluding alopecia and CTCAE grade 2 peripheral neuropathy.
13. *Patients with myelodysplastic syndrome/treatment related acute myeloid leukaemia.
14. Major surgery within 2 weeks of starting study treatment: patients must have recovered from any effects of any major surgery.
15. *Immunocompromised patients, e.g., patients who are known to be serologically positive for human immunodeficiency virus (HIV).
16. *Patients considered a poor medical risk due to a serious, uncontrolled medical disorder, non-malignant systemic disease or active, uncontrolled infection. Examples include, but are not limited to, uncontrolled ventricular arrhythmia, recent (within 3 months) myocardial infarction, uncontrolled major seizure disorder, unstable spinal cord compression, superior vena cava syndrome, extensive bilateral lung disease on High Resolution Computed Tomography scan or any psychiatric disorder that would limit ability to comply with study procedures, and any other medical condition that, in the opinion of the investigator, places the patient at unacceptable risk of toxicity.
17. *Patients with a history of treated CNS metastases are eligible, provided they meet all of the following criteria: Disease outside the CNS is present. No clinical evidence of progression since completion of CNS-directed therapy. Minimum of 2 weeks between completion of radiotherapy and Cycle 1 Day 1 and recovery from significant (Grade \geq 3) acute toxicity with no ongoing requirement for $>$ 10mg of prednisone per day or an equivalent dose of other corticosteroid.
18. *Patients unable to swallow orally administered medication and patients with gastrointestinal disorders likely to interfere with absorption of the study medication.
19. Pregnant or breast feeding women.
20. *Previous allogeneic bone marrow transplant.

21. *Patients with a known hypersensitivity to olaparib or any of the excipients of the product.
22. *Whole blood transfusions in the last 120 days prior to enrolment to the study which may interfere with *gBRCA* testing (packed red blood cells and platelet transfusions are acceptable, for timing refer to inclusion criteria no.10)

Procedures for withdrawal of incorrectly enrolled patients see Section 5.3.

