6.2.2 On treatment procedures

The visit schedule is based on 21-day cycles.

Patients will attend the clinic weekly on days 1 (1st day of treatment), 8 and 15, following the commencement of study treatment and then every 3 weeks (day 1 of every cycle) until discontinuation of treatment.

The following assessments will be performed at time points specified in the study schedule (see [Table 1](#)):

- Vital signs. Body weight is only required at day 1 of 1st day of study treatment, if it has not been assessed within 7 days of randomisation. Any other time as clinically indicated
- Haematology and clinical chemistry: Safety blood samples do not need to be repeated on Day 1 of study treatment if there have been separate assessments within 7 days before starting study treatment and which must have been 3 weeks after last dose of chemotherapy based therapy, unless the investigator believes that it is likely to have changed significantly
- Physical examination (assessments post Day 1 are not required to be captured on an eCRF, however any significant changes from baseline must be reported as an AE)
- CT of chest, abdomen and pelvis (or MRI if CT is contraindicated) performed until objective disease progression. RECIST assessments to be scheduled every 6 weeks (± 1 week) from randomisation for the first 24 weeks and then every 12 weeks (± 1 week). If progression is not confirmed by BICR an additional scan will be requested at the next scheduled visit. CT/MRI of chest, abdomen and pelvis to be performed until objective disease progression.
- ECG any time if clinically indicated
- Urinalysis any time if clinically indicated
- Serum or urine pregnancy test for women of childbearing potential (prior to treatment on day 1 of 1st day of study treatment). If the test is positive then a confirmatory test should be performed
- For patients with **known** BRCA status: *BRCA1/2* mutation status. 2 blood samples: One blood sample to test for *BRCA* mutations using the current commercial Myriad *BRCA* analysis test, and the second blood sample for a bridging study to validate the companion diagnostic test for olaparib
- AE and concomitant medications (including any blood transfusions) at every visit
- Patient Reported Outcomes and Quality of life questionnaire: EORTC QLQ-C30 at baseline (prior to randomisation once eligibility is confirmed), and then every 6 weeks until disease progression. CTSQ-16 every 6 weeks and at end of study treatment.

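### Inclusion 10 can be met on marrow and organ values drawn before the last chemotherapy dose; later safeguards leave only a small residual risk

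*Protocol*

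**What the plan says.** Section 4.1, inclusion 10: "Patients must have normal organ and bone marrow function measured within 28 days prior to administration of study treatment as defined below". The limits follow (haemoglobin, neutrophils, platelets, bilirubin, transaminases, creatinine). The window is counted back from first dose, and the date of last chemotherapy is not mentioned.

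Section 4.2, exclusion 3: "Cytotoxic chemotherapy or non-hormonal targeted therapy within 21 days of Cycle 1 Day 1 is not permitted".

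Section 4 fixes when eligibility is judged: "Each patient should meet all of the inclusion criteria and none of the exclusion criteria for this study prior to randomisation". Table 1 footnote c then separates randomisation from dosing: "It is recommended that patients commence study treatment as soon as possible after randomisation, and ideally within 3 days".

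Table 1 schedules "Haematology / clinical chemistry" at Part 2 screening (days -28 to 0) and again on Days 1, 8 and 15. Footnote e waives the Day 1 draw if a sample was taken in the 7 days before treatment, "and which must have been 3 weeks after last dose of chemotherapy". Section 6.2.2 repeats the condition: "which must have been 3 weeks after last dose of chemotherapy based therapy". In both places it applies only to a sample standing in for Day 1, not to the sample that qualifies the patient under inclusion 10.

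Two other provisions bear on the point. Exclusion 12 bars persistent toxicities of CTCAE grade 2 or worse "caused by previous cancer therapy, excluding alopecia and CTCAE grade 2 peripheral neuropathy". Section 5.3 opens by saying, without exception, that patients who do not meet the criteria are neither to be enrolled nor to be given study treatment.

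**The concern.** Inclusion 10 is there to show that marrow and organs are fit to start study treatment. A value drawn before the last cytotoxic dose cannot show recovery from that dose, yet the written rule accepts it. The protocol recognises the principle in footnote e and section 6.2.2 but does not carry it into the eligibility criterion.

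Short intervals are foreseeable. Section 6.6.2.2 wants to limit time off treatment after chemotherapy and allows BRCA testing while chemotherapy continues. Section 1.1.5 names bone marrow as the primary target organ of olaparib toxicity in animal studies.

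At stake is mainly the order of events. The count that reflects the last dose may be seen only after the patient has been allocated open-label. If it falls outside the limits, the site holds an older passing value and a newer failing one, and no sentence says outright which governs.

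**Working it through.** The protocol gives no figure to reproduce; the check is a day count.

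**Inputs**
- L = days from last cytotoxic dose to first study dose; L ≥ 21 (exclusion 3), or L ≥ 22 if day 21 itself is barred.
- s = days from qualifying sample to first dose; s ≤ 28 (inclusion 10).
- k = days from randomisation to first dose; ideally no more than 3 (footnote c).
- A sample replacing Day 1 needs s ≤ 7 and L − s ≥ 21 (footnote e, section 6.2.2).

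**Step 1: can the qualifying sample predate the last dose?** It does when s > L. The largest lead is max(0, 28 − L).

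| L (days) | Qualifying sample days that predate the dose | Largest lead (days) |
|---|---|---|
| 21 | 22–28 | 7 |
| 22 | 23–28 | 6 |
| 23 | 24–28 | 5 |
| 24 | 25–28 | 4 |
| 25 | 26–28 | 3 |
| 26 | 27–28 | 2 |
| 27 | 28 | 1 |
| 28 or more | none | 0 |

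If day 21 is barred, the first row drops out and the range is 22–27. If day 21 is allowed but day 28 is not counted, the range is 21–26. The gap exists under each of these readings.

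**Step 2: is there always a later count before dosing?** Yes. A Day 1 sample (s = 0) lies L ≥ 21 days after chemotherapy by exclusion 3, and a sample replacing it must also be 3 weeks after. Each patient therefore has a scheduled post-washout count by first dose.

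**Step 3: can that count come after randomisation?** A sample at least 21 days after chemotherapy has s ≤ L − 21. It can be drawn on or before the day of randomisation only if s ≥ k, so L − 21 ≥ k is needed. This fails as follows:

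| k | Day 21 allowed | Day 21 barred |
|---|---|---|
| 0 | none | none |
| 1 | L = 21 | none |
| 2 | L = 21–22 | L = 22 |
| 3 | L = 21–23 | L = 22–23 |

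For those intervals the footnote e count necessarily follows randomisation. For longer intervals it can come earlier, but nothing requires it to.

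**Step 4: what if the start is held?** A sample predating chemotherapy has s ≥ 22. Holding the start by h days keeps it valid only while s + h ≤ 28, so h ≤ 6 at most. At s = 28, a slip of one day expires it and forces a new, post-chemotherapy measurement.

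**The case against.** The strongest reply is that the protocol already deals with this in practice, and most of that reply stands.

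- **Later count.** A post-washout count is always scheduled by first dose (step 2), with further draws on Days 8 and 15.
- **Section 5.3.** Its opening bars treating patients who fail the criteria. Because inclusion 10 is anchored to first dose rather than to randomisation, a failing Day 1 value lies inside its window and is arguably covered. The rest of 5.3 addresses patients randomised in error, wrongly started, or failing after initiation, so the case is not named, but the opening goes a long way.
- **Room to wait.** Starting within 3 days is a recommendation, so the site can hold for recovery, and a hold soon expires the old sample (step 4).
- **Exclusion 12.** Table 3 in section 5.5.7.1 labels haemoglobin from 8 to below 10 g/dL as grade 2, so a known, persisting haemoglobin failure is excluded. Exclusion 12 orders no new count, however.
- **On-treatment rules.** Tables 3 and 4 allow olaparib to continue at the investigator's judgement at some values below the entry limits, which lessens the harm if one such dose is given.
- **Narrow scenario.** It needs qualifying bloods, then another cytotoxic dose within 7 days, then a start 21 to 27 days after that dose.

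A reader might go further and infer that patients can be dosed with no count since chemotherapy. Table 1 and footnote e rule that out. A reader might also see harm in keeping untreated patients in the Full Analysis Set, or in the deviation-bias analysis in section 12.2.2.1 not detecting these cases. The first is correct intention-to-treat practice. The second analysis concerns wrong disease or no randomised therapy received, above 10% of patients, and was not designed for this question.

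The reply does not remove the criterion's acceptance of a value that predates the exposure of concern, or the lack of an explicit rule on which value governs.

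**Conclusion.** The point holds as a minor gap in an eligibility criterion. At washouts of 21 to 27 days (22 to 27 if day 21 is barred), a patient can be randomised on values up to 7 (or 6) days older than the last cytotoxic dose. The residual risk is small: unrecovered counts may be found only after open-label randomisation, when the site must decide without an explicit rule.

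This rests on reading the 28-day and 21-day windows as written; other boundary readings shift the range by one day. The number of patients affected cannot be derived from the protocol and is probably small. Type I error, power and the primary PFS analysis method are untouched. A reader might infer a serious safety failure or a threat to the trial's result; the scheduled Day 1 count, exclusion 12 and section 5.3 do not support that. The change is an inexpensive improvement, not a necessary correction.

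**What to change.** Add to inclusion 10 that (a) the qualifying values must be the most recent before randomisation and taken after the last chemotherapy dose, and (b) the Day 1 sample, or the within-7-days sample replacing it, must meet the same limits before first dose.

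Part (a) closes the gap. Alone it would still accept a sample drawn the day after chemotherapy, so part (b) makes the post-washout count decisive and settles which value governs.

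**Cost.** The bloods in (b) are local and already scheduled. Part (a) shortens the look-back only at intervals of 21 to 27 days, from 28 days to no more than L days. Some of these patients will need a repeat draw or a short delay. Part (b) means reading the result before dosing. Neither part prevents a Day 1 failure from another cause, such as a change in disease.

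**Optional.** The screening sample itself could be required at least 3 weeks after chemotherapy. This is not needed to close the gap and costs more: the usable window becomes min(28, L − 21), which is 7 days at L = 28, 14 at 35, 21 at 42, and the full 28 only from L = 49. It would restrict every patient less than 49 days from chemotherapy, a debatable trade for a small risk.
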